WARD - Circadian analysis

Clinicaltrials.gov identifier NCT05347784

Statistical analysis plan

Version 1.1

June 9th 2023

Method

Patients

This analysis is a part of the Wireless Assessment of Respiratory and circulatory Distress (WARD) project.

The study is a nested case-control study, using patient vital sign data from 3 previous observational cohort studies of postoperative patients.

Clinicaltrials.gov identifiers:

- NCT03491137 (n=491)
- NCT04473001 (n=70)
- NCT04628858 (n=40)

All patients in the studies above have had the following vital signs recorded:

- Heart rate (HR)
- Respiration frequency (RF)
- Peripheral arterial oxygen saturation (SpO₂)
- Blood pressure (BP).

All values except BP have been recorded continuously with a 1-minute sampling rate. BP was recorded every 30 minutes during the daytime and every 60 minutes during the night.

Manual intermittent vital sign measurements were collected from electronic health records for study NCT03491137, and National Early Warning Score values will be calculated from these.

Outcomes

The primary outcome defining the case population is patients that have any postoperative serious adverse event (SAE) occurring from the start of vital sign monitoring in the ward, and up to 24 hours after vital sign monitoring. The control population will be the patients that have no recorded postoperative SAE up to 30 days after surgery. For patients with several outcomes, only measurements in the 24-hour period

preceding the first SAE were chosen for analysis. We also censored the last hour before an outcome, as this time is expected to represent the delay between clinical suspicion and confirmation by a diagnostic test for the specific SAE. For the population with no 30-day SAE, all recorded 24-hour periods were used to calculate exposure variables.

Outcomes for all studies were assessed using a standardised manual that was constructed before outcome evaluation. The definition of an SAE was taken from good clinical practice guidelines:

“any untoward medical occurrence that at any dose: – results in death,– is life-threatening,– requires inpatient hospitalisation or prolongation of existing hospitalisation, results in persistent or significant disability/incapacity, or is a medically important event or reaction.“.

Circadian definitions

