Six different ‘windows’ of circadian rhythm were defined from the literature: night-time nadir, peak-to-trough, morning activation, daytime acrophase, afternoon local minimum, and evening deactivation.

Exposures

The primary exposure is the lowest vital sign values at night-nadir, as these values are thought to represent a period of least physiologic stress, and unbiased from movement, and other voluntary activity. Secondary exposures are the lowest vital sign values at the other circadian windows. We also include manually measured NEWS values in the secondary analyses.

Analyses

We did not perform a power analysis prior to analyses due to the nested case-control design.

To avoid calculating values for circadian windows with only limited data, we introduced a minimum data condition, requiring 66 % of data for a specific window-vital sign combination.

A p-value of <0.01 was considered significant to account for multiple statistical testing.

Primary analysis

The primary analysis is descriptive

Secondary analyses

Secondary analyses were a calculation of risk ratios (RR).

For this, Youden's optimal cut-off values will be calculated for each window-vital sign combination.

Afterwards, values for each patient are split into above or below Youden's optimal cut-off point, and risk ratios will be calculated from this discrimination.

For NEWS measurements, a cut-off was defined as a total NEWS score ≥ 6 or a single-parameter score of 3.

Sensitivity analysis

We will also include calculations of fitted cosine curves to vital values, from which rhythm-adjusted mean value (MESOR) and amplitude can be calculated.

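### Cases contribute one 24-hour period and controls all of theirs, with no rule for combining control periods; a lowest value taken across them would bias the comparison

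*SAP*

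**What the plan says.** Under Outcomes, the SAP limits the case data: "For patients with several outcomes, only measurements in the 24-hour period" "preceding the first SAE were chosen for analysis". It adds: "We also censored the last hour before an outcome". For controls the rule differs: "For the population with no 30-day SAE, all recorded 24-hour periods were used to calculate exposure variables".

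Under Exposures, the statistic is a minimum: "The primary exposure is the lowest vital sign values at night-nadir", and "Secondary exposures are the lowest vital sign values at the other circadian windows".

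Under Secondary analyses, after a Youden cut-off is found for each window and vital sign, "values for each patient are split into above or below" that cut-off, and risk ratios follow. The unit is therefore the patient.

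Under Analyses, a 66% threshold applies to "data for a specific window-vital sign combination". It concerns completeness within a window and does not address how many periods a patient contributes or how they are combined.

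**The concern.** A minimum depends on how much data it is taken over. The lowest value over several nights cannot exceed the value on any one of them. If a control's nadir is the lowest across all recorded nights and a case's nadir comes from a single night, control values lie lower for a reason unrelated to physiology.

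The shift is downward for every vital sign, so its effect depends on the expected direction. Where cases are expected to have higher nadirs (HR, RF), it creates or inflates an association. Where they are expected to have lower ones (SpO2, BP), it masks the association or reverses it. The primary descriptive contrast and the Youden-based risk ratios are both exposed, in all six windows.

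**Working it through.** **Inputs from the SAP.** Cohort size 491 + 70 + 40 = 601; significance level 0.01; exposure is a lowest value; one period for cases, all periods for controls. The SAP gives no power, event or effect figure to reproduce.

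**Assumed, because the SAP does not give them.** Nights per control k = 2 to 4; between-night correlation within a patient (ICC) 0.3 to 0.9; normal nightly nadirs with total SD 1; 60 or 120 cases (about 10% or 20% of 601); no true difference. The SAP names no test, so a two-sided Mann-Whitney test stands in.

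**Step 1: null shift if the minimum is taken across nights.** Write a nightly nadir as a patient effect (variance ICC) plus a night effect (variance 1 − ICC). The minimum over k nights is the patient effect plus the smallest night effect, so controls are lower on average by

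shift = √(1 − ICC) × e_k,

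where e_k is the expected maximum of k standard normals: 0.564, 0.846 and 1.029 for k = 2, 3 and 4.

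| ICC | √(1 − ICC) | k = 2 | k = 3 | k = 4 |
|---|---|---|---|---|
| 0.3 | 0.837 | 0.47 | 0.71 | 0.86 |
| 0.5 | 0.707 | 0.40 | 0.60 | 0.73 |
| 0.7 | 0.548 | 0.31 | 0.46 | 0.56 |
| 0.9 | 0.316 | 0.18 | 0.27 | 0.33 |

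The range is 0.18 to 0.86 SD. Simulation agrees with these values (for example 0.179 at k = 2, ICC 0.9, and 0.599 at k = 3, ICC 0.5). If half the controls have one night and half have three, the shift halves: 0.5 × 0.268 = 0.13 SD at ICC 0.9 and 0.5 × 0.708 = 0.35 SD at ICC 0.3.

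**Step 2: what the shift does to a comparison (simulated, no true effect).** At k = 3 and ICC 0.9 to 0.5, the rank test rejects at 0.01 in 28% to 97% of runs with 60 cases and in 53% to 100% with 120. The median Youden risk ratio (above against below the cut-off) is 2.1 to 3.3 and 1.7 to 2.7 respectively. With one night each, rejection is about 1%.

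These risk ratios are not all due to unequal periods. Choosing the cut-off on the same data gives, with one night each, a median of 1.65 (60 cases) or 1.41 (120 cases) for the larger of RR and 1/RR. At the mild end (k = 2, ICC 0.9, 60 cases), rejection is 9% and the same folded median is 1.85, an excess of 1.85 − 1.65 = 0.20.

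**Step 3: masking.** Suppose cases truly lie 0.3 SD lower. The observed difference (case minus control) is shift − 0.3. At k = 2, ICC 0.9 it is 0.18 − 0.30 = −0.12 SD, so the effect is more than halved. At k = 3, ICC 0.5 it is 0.60 − 0.30 = +0.30 SD, so the sign is reversed.

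**Step 4: averaging nightly minima instead.** The mean shift is zero. The control SD becomes √(ICC + (1 − ICC)/k), for example √(0.5 + 0.5/4) = 0.79 at k = 4, ICC 0.5, against 1 for cases. In simulation over ICC 0.5 to 0.9 the rank test stays near nominal (0.7% to 2.1%), but unequal spread can still affect where the Youden cut-off falls.

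**Step 5: if cases also contribute several nights.** With the minimum over 2 case nights and 3 control nights, the net shift is √(1 − ICC) × (0.846 − 0.564): 0.707 × 0.282 = 0.20 SD at ICC 0.5 and 0.316 × 0.282 = 0.09 SD at ICC 0.9. With one case night the corresponding values are 0.60 and 0.27 SD. At ICC 0.5 with 60 cases, rejection falls from about 98% to about 16%.

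**The case against.** The strongest objection is that the SAP nowhere says a minimum is taken across nights. A reader might infer from the pairing of a lowest value with all control periods that the planned analysis is biased and its significant results largely artefact. The text does not support that. It leaves the combination rule open, and nightly nadirs averaged per patient would also fit. The large rejection rates and risk ratios belong to one reading only. This objection stands, and the point is conditional for that reason.

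A second inference would be that every case is explicitly limited to one period. The sentence names patients with several outcomes. A patient with a single SAE may have several monitored days before it, and read literally the SAP gives no period for that patient. Extending the rule to all cases is plausible but is an interpretation, and Step 5 shows that much of the size depends on it.

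Third, nights per control, ICC, case number, normality and test are all assumed, and the primary analysis is declared descriptive, so rejection rates are only a yardstick. That is fair, and the SD shift is the better measure. But a descriptive contrast of one-night with multi-night minima is distorted in the same way, and the direction does not depend on the assumed sizes so long as cases give one night, some controls give more than one, and nights are not perfectly correlated.

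The cosine-fit sensitivity analysis does not answer the point. MESOR is not a minimum and avoids this shift, but it is a different quantity and supplies no rule for the primary exposure.

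**Conclusion.** The concern holds in conditional form and should be fixed. It is certain from the text that the control exposure lacks a combination rule and that the stated sampling is unequal for at least some cases. Under the most literal reading, a lowest value over all control periods, the control nadirs are shifted down by about 0.2 to 0.9 SD with no true association, given one case night, 2 to 4 control nights and ICC 0.3 to 0.9. The shift is smaller if cases also contribute several nights, and it is absent in the mean if nightly minima are averaged. The documents do not show which of these was intended, so they do not establish that the results will be biased, only that the plan leaves room for it. Confidence is medium.

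The optimism from choosing the Youden cut-off on the same data is a separate matter and remains whichever rule is adopted.

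**What to change.** State in the SAP that the one-period rule applies to all cases, including those with a single SAE. State that each control contributes one 24-hour index period of the same length, with its last hour removed and the same 66% condition, chosen so that control periods match the cases' distribution of postoperative time and clock time. Repeat the draw so that all control data are used, and specify how results are pooled over draws. Rule out a minimum across control periods.

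The matching matters. In null simulations, an index night matched on postoperative night rejected in 0.3% to 1.5% of runs, with or without a postoperative trend. With an assumed trend of 0.1 to 0.2 SD per night and all case nights on night 1, an unmatched random night rejected in up to 34% (60 cases) or 62% (120 cases).

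Analysing control periods as separate rows with clustered standard errors is not an equal alternative. It departs from the per-patient split on which the risk ratios are built, and it does not balance postoperative timing.

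The cost is SAP wording and analysis code, with no new data. The downside is that some control periods are unused in any one draw, which the repeated draws offset.

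### Case and control exposure periods are not aligned on time since surgery, so postoperative recovery can be mixed with the SAE contrast

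*SAP*

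**What the plan says.** Under Patients, the SAP describes the design: "The study is a nested case-control study, using patient vital sign data from 3 previous observational cohort studies of postoperative patients". The three cohorts hold 491 + 70 + 40 = 601 patients.

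Under Outcomes, a case is a patient with an SAE "occurring from the start of vital sign monitoring in the ward, and up to 24 hours after vital sign monitoring", so the postoperative day of the SAE can differ from case to case. For cases, only measurements in the 24-hour period "preceding the first SAE were chosen for analysis". That sentence is worded for patients with several outcomes, but no other rule for cases is given, and I read it as applying to all of them. The SAP adds: "We also censored the last hour before an outcome".

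Controls are defined in the same section: "The control population will be the patients that have no recorded postoperative SAE up to 30 days after surgery". Their exposure period is: "For the population with no 30-day SAE, all recorded 24-hour periods were used to calculate exposure variables".

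Under Exposures: "The primary exposure is the lowest vital sign values at night-nadir". Under Secondary analyses, "values for each patient are split into above or below Youden's optimal cut-off point, and risk ratios will be calculated from this discrimination".

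**The concern.** Cases are anchored to an event and controls to nothing. A case supplies whichever postoperative day precedes its SAE. A control supplies every recorded day, from the first to the last of its monitoring. Vital signs in surgical patients may well change over these days as the effects of anaesthesia, opioids, fluids, oxygen and pain recede. If they do, and if case nights sit earlier or later in the course than control nights, the night-nadir comparison partly compares recovery days. The same difference would pass into the Youden cut-offs, which are chosen to separate the two groups whatever the source of the separation, and from there into the risk ratios.

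This is a different matter from the unequal number of periods per patient. It would remain if each control supplied one randomly chosen night, or the mean of its nights. What is at stake is whether a difference in night nadir can be read as a marker of an impending SAE.

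**Working it through.** **Does anything in the SAP repair it?** The six circadian windows and the fitted cosine curves deal with time of day, not days since surgery. The 66 % rule deals with missing data. The risk ratio is described as a plain split at the cut-off. No index time for controls, risk set, matching, stratification or adjustment by postoperative day is stated.

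**Size.** The SAP gives no figure on this point to reproduce. Number of nights, SAE timing, drift and case fraction below are assumptions.

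*Step 1, gap in mean night.* With 4 monitored nights counted equally, controls average (1+2+3+4)/4 = 2.5. If case nights are distributed 40/30/20/10 %, cases average 0.4×1 + 0.3×2 + 0.2×3 + 0.1×4 = 2.0. The gap is 0.5 night.

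*Step 2, spurious shift.* d = gap × drift per night. Drifts of 0.1, 0.2 and 0.5 SD per night give d = 0.05, 0.10 and 0.25 SD.

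*Step 3, risk ratio with no true association.* Take 20 % cases, a split at the control median and normal values. With Φ(d) the share of cases on the shifted side,

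RR = [0.2Φ(d) / (0.2Φ(d) + 0.4)] / [0.2(1−Φ(d)) / (0.2(1−Φ(d)) + 0.4)].

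- d = 0.05: (0.104/0.504) / (0.096/0.496) = 1.07
- d = 0.10: (0.108/0.508) / (0.092/0.492) = 1.14
- d = 0.25: (0.120/0.520) / (0.080/0.480) = 1.38

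*Step 4, other timings.*

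- SAEs late, gap −0.5 night: the ratios invert, to 1/1.07 = 0.94 and 1/1.38 = 0.73 at the ends of the range.
- Two nights only, with the 40:30 ratio kept: cases average (4×1 + 3×2)/7 = 1.43 against 1.50, a gap of 0.07 night. The same drifts give RR about 1.01-1.05.
- No drift, or equal night distributions: d = 0 and RR = 1.

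**Simulation under the null**, also on assumed inputs: 100 cases, 350 controls, 4 nights, SD 10 bpm between patients and 5 bpm between nights, Welch test at two-sided 0.01, 1500 repetitions. Case nights were weighted 50/30/15/5 % (early), equally, or 5/15/30/50 % (late). Controls were summarised by the mean of their nights.

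| Heart-rate trend per day | Spurious difference, SAEs early | SAEs late | False-positive rate (nominal 1 %) |
|---|---|---|---|
| 0 | about 0 | about 0 | about 1 % |
| −1 bpm | +0.8 bpm | −0.8 bpm | about 3 % |
| −2 bpm | +1.5 bpm | −1.5 bpm | about 8 % |
| −3 bpm | +2.2 bpm | −2.2 bpm | 19-20 % |

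This agrees with direct arithmetic: the early weights give a mean night of 0.5 + 0.6 + 0.45 + 0.2 = 1.75, a gap of 0.75 night, and 0.75 × 1, 2, 3 = 0.75, 1.5, 2.25 bpm. With case nights spread equally the rate stayed near 1 % at every trend. With control nights drawn from the case-night distribution, the difference was between −0.06 and +0.04 bpm and the false-positive rate 0.7-1.4 % in every scenario.

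**The case against.** A reader might infer that recovery is in fact confounding this comparison, and that it makes cases look worse. The SAP does not support that. It reports neither a trend over nights nor the timing of SAEs, and two of its own rules weaken an assumption of early clustering. An SAE before the first monitored night has no recorded night nadir in its preceding 24 hours, and the 66 % rule drops cases with too little of the window; both remove the earliest SAEs from the primary exposure. Admitting SAEs up to 24 hours after monitoring adds cases whose data come from its end. Neither rule excludes early clustering, but the direction is open.

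The upper end of the range is also generous. A drift of 0.5 SD per night is 1.5 SD from the first to the fourth night. The simulated trends of 1-3 bpm, on a total SD of √(10² + 5²) = 11.2 bpm, are only 0.09-0.27 SD per night. The calculation also splits at the control median, whereas the SAP splits at the Youden cut-off. These points stand and are why the range must reach down to no bias and to reversed bias.

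It can further be said that a nested case-control study need not match on postoperative day, that the primary analysis is only descriptive, and that all control days are a fair reference if the aim is discrimination across ward days. This is a legitimate choice of target. But a descriptive contrast between groups is open to the same mixing, and a reader of the risk ratios could not tell which of the two was measured.

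One simulated result should not be counted here. If controls were summarised by the lowest value over all their nights, the spurious difference was about 5 bpm (false-positive rate about 93 %) with no trend at all. That comes from taking a minimum over more nights, a separate problem: the SAP does not say how several control nights become one value.

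**Conclusion.** The concern holds as a conditional one. The SAP itself fixes event-anchored periods for cases and unanchored periods for controls, so this is a stated rule and not a detail left to the protocol, and nothing in the SAP corrects for it. Bias requires both a trend over postoperative nights and different night distributions in the two groups. For early SAEs over 4 nights, with a 0.5-night gap and a drift of 0.1-0.5 SD per night, the spurious risk ratio is about 1.07-1.38; it is inverted if SAEs come late, close to 1 with two nights, and absent if either condition fails. All these inputs are assumed. The SAP should be changed because the remedy is cheap and would show whether the problem is present, not because bias has been demonstrated.

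**What to change.** 1. Index every window by postoperative night. Surgery dates are already needed to apply the 30-day control definition.
2. Report the distribution of postoperative night for cases and for controls, and give the primary descriptive comparison by night, pooling late nights (for example night 3 or later).
3. Derive one pooled Youden cut-off per vital sign and window. Separate cut-offs by night would be sparse across up to 4 × 6 = 24 combinations, and the resulting risk ratios would not be comparable.
4. Beside the crude risk ratios, report ratios with controls weighted or frequency-matched to the case-night distribution, or Mantel-Haenszel ratios over pooled nights.

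The cost is SAP wording and one merge on postoperative day, with no new data. The downside is few patients on late nights and some loss of precision.

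### The SAP says p<0.01 accounts for multiple testing but names no family or error rate; over its 24 planned risk ratios the chance of a false positive is about 21% even with independent tests and valid p-values

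*SAP*

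**What the plan says.** The significance rule is one sentence in the SAP's Analyses section: "A p-value of <0.01 was considered significant to account for multiple statistical testing". No family of tests, error rate or derivation of 0.01 accompanies it, and no test is named anywhere in the SAP.

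The other relevant statements are these:

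- Under Primary analysis: "The primary analysis is descriptive".
- Under Exposures: "The primary exposure is the lowest vital sign values at night-nadir". The other windows are secondary, and "We also include manually measured NEWS values in the secondary analyses".
- Under Circadian definitions, six windows "of circadian rhythm were defined from the literature: night-time nadir, peak-to-trough, morning activation, daytime acrophase, afternoon local minimum, and evening deactivation".
- Under Secondary analyses, Youden's "optimal cut-off values will be calculated for each window-vital sign combination". Patients are then divided at Youden's "optimal cut-off point, and risk ratios will be calculated from this discrimination". NEWS has a cut-off fixed in advance.

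**The concern.** The sentence gives both a rule and a justification, and the justification cannot be checked. A per-test threshold accounts for multiplicity only relative to a stated set of tests and a stated error rate, and the SAP gives neither. Followed as written, it allows any of 24 or 25 risk ratios with p<0.01 to be reported as significant after allowance for multiplicity.

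A second feature makes the statement less safe. Each cut-off is chosen because it best separates cases from controls, and the risk ratio is then computed on that same split. A p-value from such a split that ignores the choice of cut-off is too small, so its nominal 1% is not its real error, even for one test.

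**Working it through.** **Inputs.** Threshold 0.01 (SAP, Analyses). Six windows (Circadian definitions). Four vital signs: heart rate, respiration frequency, SpO₂ and blood pressure (Patients). One cut-off and one risk ratio per pair of window and vital sign (Secondary analyses). One NEWS comparison. The SAP states no family-wise figure, so there is none to reproduce.

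**Count.** 6 × 4 = 24, with blood pressure counted once; 24 + 1 = 25 with NEWS. If blood pressure were analysed as two components (an assumption), 6 × 5 = 30.

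**Step 1: independent tests, valid p-values, no true associations.** P(at least one p below α) = 1 − (1 − α)^m.

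| Tests m | α | Result |
|---|---|---|
| 4 (night nadir only) | 0.01 | 3.9% |
| 5 | 0.01 | 4.9% |
| 24 | 0.01 | 21.4% |
| 25 (with NEWS) | 0.01 | 22.2% |
| 30 (two BP components) | 0.01 | 26.0% |
| 24 | 0.05 | 70.8% |

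The threshold therefore does reduce the error. If the target were 5% family-wise (an assumption, since the SAP states none), 0.01 is the Bonferroni level for 0.05/0.01 = 5 tests, and no set in the SAP has five. For 24 tests the level would be 0.05/24 = 0.0021.

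**Step 2: correlated tests, p-values still valid.** The SAP gives no correlations, so a range was assumed. Simulation: 200,000 draws of 24 normal statistics in four blocks of six, counting any |z| > 2.576.

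- Within-block correlation 0.5 / 0.7 / 0.9, none between blocks: 18.2% / 14.9% / 9.7%.
- The same with between-block correlation 0.3: 16.1% / 13.6% / 9.1%.
- One common correlation of 0.8 across all 24: 6.6%.
- One common correlation of 0.9 across all 24: 4.2%. This is the only setting tried that falls below 5%, and it requires the four different vital signs to be almost interchangeable.

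**Step 3: p-values from same-data Youden splits.** Null simulation, 3,000 data sets per setting. Assumed: N = 300 or 600, 10% or 30% cases, a chi-square test on each split, and (within-sign, between-sign) correlations of (0, 0), (0.5, 0), (0.9, 0), (0.7, 0.3) and (0.8, 0.8). Fixed direction means that the high-risk side of the cut-off is set beforehand; free direction means that either side may be chosen.

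| Share of null results with p below the threshold | Fixed direction | Free direction |
|---|---|---|
| One test, 0.01 | 6–8% | 12–14% |
| Any of 4 night-nadir tests, 0.01 | 18–28% | 32–45% |
| Any of 24 tests, 0.01 | 44–86% | 70–97% |
| Any of 24 tests, 0.05/24 | 17–47% | 32–64% |

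The last row shows that a stricter threshold on these p-values would not repair the claim.

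**The case against.** The SAP claims neither family-wise control nor a 5% level, so it is not fair to hold it to one. By the figures above, 0.01 brings 70.8% down to 21.4%, which could be called imprecise rather than false. No p-value is explicitly attached to the risk ratios; the rule might be meant for case–control comparisons within the descriptive analysis or for the cosine-fit quantities in the Sensitivity analysis. Night nadir is the primary exposure, and for its four tests 0.01 gives 3.9%. The 21% assumes independence and valid p-values, and neither is likely to hold exactly. The Youden problem is distinct from multiplicity, since it affects a single test. And all of this concerns secondary analyses.

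Much of this stands as qualification. The 5% target is an assumption, the 24-test family is inferred from the only set of comparisons that the SAP specifies, and 21% is a benchmark rather than an estimate. If the rule is meant for other comparisons, the Youden figures do not apply. But the family and the error rate are unnamed on any reading. The night-nadir defence needs a restriction that the SAP does not make. It also needs valid p-values, which the Youden splits do not give. The Youden step belongs here because it rules out the obvious repair of simply tightening the threshold.

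**Conclusion.** The concern holds: the sentence is wrong as written. It asserts an allowance for multiplicity that no stated family or error rate supports.

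Over the 24 risk ratios, 0.01 leaves a 21.4% chance of at least one false positive if tests are independent and p-values valid. With valid p-values and the assumed positive correlations it is about 7–18%, lower only in the extreme case of a common correlation of 0.9. If the p-values come from the Youden splits, it is 44–86% or 70–97% depending on direction. Those last ranges rest on the assumed test, sample size, case share and correlations, and all the figures suppose that no true association exists.

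The absence of a family and an error rate is certain; which of these figures applies depends on which tests were meant. The descriptive primary analysis is not affected. What is at stake is the wording of significance in the secondary results, and it should be corrected.

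**What to change.** **Recommended.** Delete the statement that 0.01 accounts for multiple testing and replace it with a paragraph to this effect:

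> All risk ratios, including that for NEWS, are exploratory. They are reported with confidence intervals, night nadir first, and no claim of statistical significance is made. The intervals are not adjusted for multiplicity. For the 24 risk ratios based on Youden cut-offs, neither estimates nor intervals allow for the choice of cut-off on the same data; the NEWS cut-off was fixed in advance.

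This fits the descriptive primary analysis and needs no new programming. The cost is one paragraph, and that no risk ratio is called significant.

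**Optional, if significance claims are wanted.** Name the family, say whether NEWS is in it, state the error rate and level, and use a permutation max-statistic that re-selects every cut-off in each permutation. This has three prerequisites:

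- Case and control values must be summarised over comparable periods. Under Outcomes, cases contribute the 24 hours before the first SAE and controls contribute all their recorded 24-hour periods, so the control exposure definition would have to change.
- A rule is needed for windows lost under the condition "requiring 66 % of data for a specific window-vital sign combination".
- NEWS needs a decision, because the manual measurements come from one cohort only (n=491).

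The program must also be written and checked. Holm or a smaller threshold applied to the unadjusted Youden-split p-values is not an adequate substitute.

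### A single Youden cut-off per window and vital sign, with no risk side fixed in advance, describes only a one-directional relation; if both low and high HR, RF or BP carry risk, one tail is counted as low risk.

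*SAP*

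**What the plan says.** Under Secondary analyses, the SAP says that Youden's "optimal cut-off values will be calculated for each window-vital sign combination". Then "values for each patient are split into above or below" that point, and "risk ratios will be calculated from this discrimination". The rule is the same for HR, RF, SpO2 and BP in all six windows, which makes 6 × 4 = 24 combinations if BP counts as one series.

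The exposure is always a minimum. Under Exposures: "The primary exposure is the lowest vital sign values at night-nadir", and "Secondary exposures are the lowest vital sign values at the other circadian windows". The outcome is "any postoperative serious adverse event (SAE) occurring from the start of vital sign monitoring in the ward" (section Outcomes), up to 24 hours after monitoring ends, with all event types together.

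Only the NEWS cut-off has a direction set beforehand. For the four vital signs the SAP names no exposed side, has no low/middle/high grouping, and does not examine the shape of the relation. Significance is set at p<0.01.

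**The concern.** An above/below split assumes that risk rises or falls in one direction with the value. With a pooled outcome that assumption needs support for HR, RF and BP, because different events could follow abnormally low or abnormally high values. A minimum records low extremes directly, and a patient whose minimum is itself high still falls on the above side, so both tails remain in the data. SpO2 is left out of this point.

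If both tails carry risk, the cut-off isolates one of them and pools the other with the normal middle as the reference group. With no direction fixed, the data choose which tail is reported. The RR is the only measure of association the SAP names for these exposures, so a reader could take a risk-carrying range of values to be safe.

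**Working it through.** The SAP gives no event count, cut-off or RR, so there is no planned figure to reproduce.

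**Inputs from the SAP.** Patients: 491 + 70 + 40 = 601. This is an upper bound, since the 66% data condition removes values, and patients whose only SAE comes later than 24 hours after monitoring but within 30 days are neither cases nor controls. Significance level: 0.01.

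**Assumed, not in the SAP.** 20% cases; outer 15% tails on each side at twice the risk of the middle 70%; one value per patient.

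**Step 1: what one cut-off placed at a tail limit reports.**
- Middle risk: 0.20 / (0.70 + 0.15×2 + 0.15×2) = 0.20 / 1.30 = 0.154.
- Tail risk: 2 × 0.154 = 0.308.
- Risk in everyone outside the chosen tail: (0.70×0.154 + 0.15×0.308) / 0.85 = 0.181.
- RR of chosen tail versus the rest: 0.308 / 0.181 = 1.70, against a true tail-versus-middle RR of 2.
- Share of all cases in the unchosen tail: 0.15×0.308 / 0.20 = 23%.

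**Step 2: the SAP's rule, simulated.** The cut-off maximises |sensitivity + specificity − 1| with direction free, and the RR and a two-by-two test follow from the split.
- Median RR is about 1.9 in the base case. It exceeds 1.70 because the cut-off is tuned to the same data: dilution by the second tail and optimism from selection partly offset each other. With tails of 10% or 20% and middle-zone risks of 8% or 15%, the median was 1.84 to 2.12 for a true RR of 2, and 2.20 to 2.79 for a true RR of 3.
- Across those scenarios, essentially the whole opposite tail fell in the low-risk group, and it held 14% to 31% of all cases.

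**Step 3: direction chosen.**

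| Assumed relation | Result |
|---|---|
| Equal tails | 48–52% for each side |
| No association | 51% / 49% |
| Tails at 2.5 and 1.75 times the middle, 20% cases | stronger tail in about 94% |
| Tails at 3 and 2 times the middle | stronger tail in 90% |
| One tail only, 3 times the middle | correct side in about 100% |

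**Step 4: error rate and power at p<0.01.**
- No association: the Youden split reaches nominal p<0.01 in about 13% of runs (9% to 13% across the runs made), against 1% for a 2-df spline.
- Equal tails, 20% cases: the split reaches nominal p<0.01 in 91% of runs, a figure that includes this inflation. Held to a true 1% error rate, its power is about 56% when the p-value of the split is calibrated (another calibration gives 29%). The 3-knot spline has about 72%.

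**The case against.** The strongest reply is that the SAP nowhere says that both low and high values precede SAEs. Tail sizes, tail risks and the case share are all assumed. Taking the lowest value in each window softens the high tail. If risk runs one way, the rule finds the right side and a sensible RR. All of this stands, and it is why the point is conditional.

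A reader might go further than the document allows in five ways.

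- *The direction is always arbitrary.* It is so only with near-equal tails or no association.
- *The split would be almost blind to a two-tailed relation.* That does not follow. The SAP's Youden split often reaches nominal p<0.01. Its faults are an inflated error rate and a description of one tail only.
- *The RR would be badly wrong.* For a true RR of 2 the median is near 2, although for the reason given in the working.
- *The same vital sign would look harmful when high in one window and when low in another, purely by chance.* The windows are measured in the same patients, so their directions are linked. Assuming a between-window correlation of 0.8, directions disagreed in about 21% of runs with equal tails and 11% with tails at 2.5 and 1.75. Independent coin tosses would give 50%. The true correlation is unknown, so this is not part of the point.
- *The SAP's rationale says that a raised nadir is the danger.* The Exposures section says only that "these values are thought to represent a period of least physiologic stress"; it states no direction of risk.

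It can also be said that a spline answers a different question from a threshold. That is fair, and it is why the cut-off RR need not be removed.

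**Conclusion.** The point holds in conditional form. The rule as written can represent only a one-directional relation, and no side is fixed for any vital sign. If both tails of HR, RF or BP carry risk, one tail is reported and the other is placed in the low-risk group. That tail holds 23% of cases in the base case and 14% to 31% over the other equal-tail scenarios. With unequal tails the direction is mostly stable, but the weaker tail is still mislabelled: it held about 20% of cases with tail risks of 3 and 2 times the middle.

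Apart from the shape of the relation, choosing cut-off and direction on the same data raises the nominal 1% error rate to about 13% per combination. The spline's power advantage (about 72% against 56%) is claimed only for equal tails at 20% cases, and its size depends on the calibration.

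The primary analysis is descriptive and is untouched. This should be changed, but it does not undermine the study.

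**What to change.** In the Secondary analyses section:

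1. State the expected risk direction for each vital sign before analysis.
2. For HR, RF and BP in every window, add a model of SAE status on the continuous value with a 3-knot restricted cubic spline. Use its overall 2-df test as the test of association and plot the curve. Alternatively, use three groups (low, middle, high) with limits specified in advance and the middle as reference.
3. Report the single-cut-off RR as descriptive, or use it only where a one-directional relation was stated in advance.

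The cost is a few sentences and one extra model per combination (3 × 6 = 18 for HR, RF and BP). No new data are needed. If the relation is in fact monotone, the spline spends one extra degree of freedom and loses some power.
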